1. DOCUMENT HISTORY

Version	Date	Change to previous version
1.0	2019-03-19	No previous version
2.0	2019-05-08	Final version

2. LIST OF ABBREVIATIONS

ACT	activated clotting time
aPTT	Activated partial thromboplastin time
CE	Certification
CI	Confidence interval
CRF	Case report form
DOAC	Direct oral anticoagulants
FPFV	first patient signing informed consent
ICH	International conference on harmonisation
ITT	Intent-to-treat
IVD	In vitro diagnostic test
LC-MS/MS	Liquid chromatography coupled with tandem mass spectrometry
POC	point of care
PPS	Per protocol set
PT	Prothrombin time
SAP	Statistical analysis plan
SAW-CT	Surface Acoustic Waves
SD	Standard deviation

Confidentiality Statement

This document is confidential and proprietary to Sponsor and HLZ Medizinische Statistik and for restricted circulation and access only. No part of it may be transmitted, reproduced, published or used by any person/s without prior written authorization.

Sponsor Name: DOASENSE GmbH
Statistical Analysis Plan (SAP)
Version No.: 3 Date: 2019-05-15

Sponsor Study No.: DOA-CS-002
ClinicalTrials.gov ID: NCT03182829
HLZ Medizinische Statistik Study No.: 1-2019

5. INTRODUCTION

Direct oral anticoagulants (DOACs) such as dabigatran, rivaroxaban, apixaban, and edoxaban are approved in many countries for prevention of ischemic stroke in patients with atrial fibrillation, prophylaxis of postoperative venous thromboembolism following elective knee or hip replacement surgery, treatment of acute venous thromboembolism, prolonged prophylaxis to prevent recurrent thromboembolic events and even management of acute coronary syndrome (1).

For all indications, DOACs can be administered in fixed doses, without the need for routine laboratory-guided dose adjustment. Consequently, routine plasma samples were not collected to assess anticoagulation status in the pivotal studies, but were only drawn in specific patient subgroups. However, it is important to measure anticoagulation in some patient populations, such as prior to surgery, when renal function deteriorates, during bleeding or thrombotic episodes, and to assess adherence to therapy (2). DOACs prolong coagulation or clotting times to different degrees in several clotting assays (3).

DOACs inhibit factor Xa or thrombin, which can be detected with chromogenic substrate assays. The oral direct factor Xa inhibitors rivaroxaban, apixaban and edoxaban also prolong the prothrombin time (PT) and activated partial thromboplastin time (aPTT) to different degrees depending on the DOAC and the sensitivity of reagents (3). PT and aPTT are also affected by pathological conditions in various diseases, which can reduce their specificity to anticoagulants such as DOACs. The main advantage of PT and aPTT is that they can be routinely performed in all laboratories around the clock (4).

Heptest, heptest STAT (5) are more useful for measurement of direct oral factor Xa than PT/aPTT and hemoclot (6), thrombin clotting time, and ecarin clotting time tests (7) for determination of oral direct thrombin inhibitors. These more specific tests also have their limitations. For example, Hemoclot test results were highly variable in patients undergoing

Confidentiality Statement

This document is confidential and proprietary to Sponsor and HLZ Medizinische Statistik and for restricted circulation and access only. No part of it may be transmitted, reproduced, published or used by any person/s without prior written authorization.

mechanical artificial heart valve replacement and receiving 150 mg to 300 mg bid dabigatran, despite exact timing of blood sampling for coagulation analyses, (8) indicating its limited analytical sensitivity and specificity in this clinical setting. Furthermore, these are specialized tests and can only be performed in specialist laboratories at defined times (usually normal working hours).

Chromogenic assays are based on the specific inhibition of factor Xa or thrombin in the presence of enzyme-specific chromogenic substrates. These assays determine the effect of oral direct factor Xa inhibitors rivaroxaban, apixaban, edoxaban (9), and of the oral direct thrombin inhibitor dabigatran (10). DOAC measurement needs to be carefully standardized for each individual chromogenic substrate method using specific calibrators for every DOAC, and these calibrations need to be performed with every coagulation platform. This makes specific chromogenic assays time consuming and restricts their availability and when they can be performed. The availability of the specific coagulation assays for DOACs ranges from less than 2% to 39% in coagulation laboratories, and much less in smaller laboratories and community hospitals (11). Qualitative DOAC detection from coagulation parameters gave results below, within, and above the normal range, but the assay sensitivities and specificities were still low (11).

Liquid chromatography coupled with tandem mass spectrometry (LC-MS/MS) is the gold-standard assay for DOAC quantitative assessment (12, 13). This method is used to compare the sensitivity and specificity of chromogenic substrate assays and of coagulation assays for DOACs (13). These investigations showed a high correlation of DOAC quantification between LC-MS/MS and chromogenic substrate assays and Hemoclot (Pearson correlation $r > 0.95$). Other analyses of plasma samples from patients receiving therapy with these anticoagulants have revealed only a sensitivity and specificity of 50% to 80% (14). However, these methods can only be performed in a small number of specialized laboratories, so their availability remains very limited (15).

Confidentiality Statement

This document is confidential and proprietary to Sponsor and HLZ Medizinische Statistik and for restricted circulation and access only. No part of it may be transmitted, reproduced, published or used by any person/s without prior written authorization.

To detect DOACs in blood samples in emergency situations, point of care (POC) coagulometer instruments may offer advantages over conventional clotting assays. However, the results from plasma samples of patients receiving dabigatran and rivaroxaban are variable, which limits their usefulness in acute clinical conditions (16). A whole-blood clotting time assay based on Surface Acoustic Waves (SAW-CT) has been evaluated in stroke patients treated with phenprocoumon, dabigatran, rivaroxaban, and apixaban. This assay can determine the anticoagulant level in patients receiving dabigatran, rivaroxaban, and phenprocoumon, but not apixaban (17). The *Hemochron Signature* system uses testing cards that measure the activated clotting time (ACT) and PT, and determines blood coagulation by photo-detection. The ACT and PT are prolonged in the presence of vitamin K antagonists, DOACs, and heparins if reagents do not contain heparin neutralizers. They can be used to qualitatively rule out the presence of clinically relevant concentrations of rivaroxaban and dabigatran, with sensitivities of 96% and 98% but with low specificities of 67% and 66%, respectively (18). The *Cascade Abrazo* POC test system includes specific testing cards and is currently under development. This blood test will detect inhibitors to thrombin and factor Xa and is based on photo-detection of coagulation (19). Perosphere Technologies offers a broad array of anticoagulant testing, including DOACs, unfractionated heparin, low molecular weight heparin, fondaparinux, and warfarin using a broad-spectrum POC coagulometer (20).

The certified in vitro diagnostic medical device (IVD) *DOAC Dipstick* was developed based on the rationale that DOACs are excreted into and may be detectable in the urine (21). When detecting DOACs in urine, it is important to consider that plasma coagulation proteins will not be present, unlike in blood or plasma samples. This may be an advantage because blood cells, plasma proteins, and naturally-occurring coagulation inhibitors will not be able to interact with DOACs and may not interfere with the results of the *DOAC Dipstick* (22). This test gives qualitative results regarding the absence or presence of DOACs in a patient's urine sample for both direct oral factor Xa inhibitor and oral thrombin inhibitors. This single-use assay has a

Confidentiality Statement

This document is confidential and proprietary to Sponsor and HLZ Medizinische Statistik and for restricted circulation and access only. No part of it may be transmitted, reproduced, published or used by any person/s without prior written authorization.

Sponsor Name: DOASENSE GmbH
Statistical Analysis Plan (SAP)
Version No.: 3 Date: 2019-05-15

Sponsor Study No.: DOA-CS-002
ClinicalTrials.gov ID: NCT03182829
HLZ Medizinische Statistik Study No.: 1-2019

turnaround time of 10 min and results can be determined by visual identification of specific colors with the naked eye.

This trial is conducted to assess the performance and handling of the IVD for oral direct Factor Xa and Thrombin inhibitors from urine samples of patients on treatment with DOACs in an actual point-of-care setting in comparison to results obtained by liquid chromatography-tandem mass spectrometry (LC-MS/MS) from urine samples.

6. STUDY OVERVIEW

6.1 Design Overview

This prospective, open-label, controlled, not randomized, multicenter, national Post Marketing Study in Germany.

The Post Marketing Study will be conducted at the patient's family doctor or medical practice/outpatient care unit (referred to as "investigational site" in the following).

The Post Marketing Study will consist of a single visit, which is performed during a routine visit at the investigational site.

The Post Marketing Study starts with first patient signing informed consent (FPFV) and ends with the last patient providing the last sample (last patient last visit, LPLV). Each patient will participate for approximately 1 to 2 hrs in the Post Marketing Study.

6.2. Determination of Sample Size

Two groups of medications (Thrombin inhibitor, Factor Xa inhibitors) will be tested with the IVD and test results compared to LC-MS/MS results in urine.

The objective of the investigation is to show that the proportion of false negative and false positive tests with the IVD is below 5%.

Confidentiality Statement

This document is confidential and proprietary to Sponsor and HLZ Medizinische Statistik and for restricted circulation and access only. No part of it may be transmitted, reproduced, published or used by any person/s without prior written authorization.

To improve the strength of the study result, the following adjustments were made in the version 3.0 of the SAP compared to the version 2.0: $\alpha=0.01$ and a 2-sided test with a null proportion of 0.01.

The re-calculation of the required sample size remained unchanged compared to version 2.0 of the document to show that the assumed rate of 2.5% false-negative/false-positive tests is statistically significantly lower than 5% would require 440 patients per each test group including an assumed drop-out rate of 12%, with $\alpha=0.01$ and $\beta=0.20$ (80% power).

This sample size has been assessed with the SAS procedure PROC POWER (SAS Institute Inc., Cary, NC, USA, release 9.3) using the ONESAMPLEFREQ statement under the assumption that the test will be conducted as a 2-sided test with a null proportion of 0.01.

Remark to the calculation of the anticipated dropout rate: **As the present post marketing study is a non-invasive investigation, the dropout rate may be lower than expected.** Only patients fulfilling all of the inclusion criteria and none of the exclusion criteria will be included. Patient's written informed consent is part of the inclusion criteria.

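### The 80% power is for one comparison, while the objective covers two error rates in two drug classes and no rule says which must succeed

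*SAP*

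**What the plan says.** Section 6.2 (Determination of Sample Size) sets up two classes: "Two groups of medications (Thrombin inhibitor, Factor Xa inhibitors) will be tested with the IVD and test results compared to LC-MS/MS results in urine". It gives the aim as follows: "The objective of the investigation is to show that the proportion of false negative and false positive tests with the IVD is below 5" per cent. The calculation is meant to show that "the assumed rate of 2.5% false-negative/false-positive tests is statistically significantly lower than 5" per cent, and it "would require 440 patients per each test group including an assumed drop-out rate of 12" per cent, with alpha 0.01 and 80% power. The size was obtained "using the ONESAMPLEFREQ statement", which handles one proportion against one null value. The same section adds that "the test will be conducted as a 2-sided test with a null proportion of 0.01".

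Elsewhere in the SAP:

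- Section 10.1.5 has the false-negative and false-positive proportions reported for each diagnostic test with confidence intervals, and sets a general two-sided level of 0.01.
- Section 10.2.1 describes the primary variable as true negative rates for both classes. It lists a cut-off, McNemar test, kappa, sensitivity, specificity and predictive values with 95% intervals. It contains no test against 5%.
- Section 18, tables 7 and 8, presents correct and false results with p-values separately for group A and group B.

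No section gives a joint power or a rule for when the objective counts as met.

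**The concern.** Two error rates in two classes make up to four comparisons with 5%. The calculation powers one of them. A sponsor reading 80% as the chance of meeting the objective would be misled on any reading that needs both classes to succeed.

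The missing rule matters in both directions. If every rate must pass, no alpha adjustment is needed, but the joint power falls below the single-comparison figure. If one passing rate is enough for a claim, power is not the difficulty, but the level of a single test no longer describes the overall error. If some rates pass and others do not, the SAP does not say what is concluded, so the choice could be made after the data are seen.

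**Working it through.** **Inputs from section 6.2:** limit p0 = 0.05; assumed rate p1 = 0.025; two-sided alpha 0.01; power 0.80; 440 per group including 12% drop-out, so 440 × 0.88 = 387 evaluable.

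**1. The plan's own figure.** One-sample z-test: n = [(z_alpha·√(p0(1−p0)) + z_power·√(p1(1−p1)))/(p0−p1)]².

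- Stated inputs: [(2.576 × 0.2179 + 0.842 × 0.1561)/0.025]² = 768 evaluable, and 768/0.88 = 873 per group.
- Null of 0.01 in place of 0.05, two-sided 0.01: 669 evaluable, 761 per group.
- Null of 0.01, one-sided 0.05: 387 evaluable, 440 per group.
- Null of 0.05, one-sided 0.05: 384 evaluable, 437 per group.

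So 440 is not reproduced at two-sided 0.01 with this test. That is a separate fault, but it decides which per-comparison power belongs in the joint calculation.

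**2. Joint power, taking 0.80 per comparison at face value.**

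- One rate per class, two classes of different patients: 0.80² = 0.64.
- All four rates, independent: 0.80⁴ = 0.41.
- All four rates, groups independent, any dependence within a group: one pad's false-negative rate and the other pad's false-positive rate can come from the same patients. The chance that both pass in a group then lies between 0.80 + 0.80 − 1 = 0.60 and 0.80. Over two groups this gives 0.60² = 0.36 to 0.80² = 0.64.
- Power needed per comparison for 80% jointly on four independent rates: 0.80^(1/4) = 0.946.

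**3. Joint power at the stated alpha, 5% limit and sample size.** Assumption: each rate has 387 evaluable patients in its denominator. With an exact binomial test and a lower tail of at most 0.005:

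- P(X ≤ 8 | 0.05) = 0.0026 and P(X ≤ 9 | 0.05) = 0.0062, so the critical count is 8.
- Power is P(X ≤ 8 | 0.025) = 0.368 (z-approximation 0.33).
- Two independent comparisons: 0.368² = 0.135.
- Four independent comparisons: 0.368⁴ = 0.018.
- Four comparisons, groups independent, any dependence within a group: between 0 (because 2 × 0.368 < 1) and 0.368² = 0.135.

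**4. Error if any one success may be claimed.** Only the lower tail can support a claim of being below 5%, so each test contributes 0.005. With all four true rates at 5%, 1 − 0.995⁴ = 0.020 under independence, and 4 × 0.005 = 0.020 bounds it under any dependence. That is four times the 0.005 of a single test.

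**The case against.** The strongest reply is that the SAP never asks for four passes. Section 6.2 uses the singular for the proportion and joins the two error types with a slash, so it may mean one combined error rate per group. It also ties the 80% to the size of each test group and does not call it the chance that both classes succeed. Section 6.2.1 only asks for an assessment of diagnostic performance, and 10.2.1 names true negative rates with no test against 5%.

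Much of this stands. A reader might infer that the objective requires all four rates and that the real power is therefore 41%. The text does not establish that requirement, and 41% also needs independence. A reader might also infer that some rates failing is the likelier outcome even if the strip performs as assumed. At 80% each, that holds for four independent rates (1 − 0.41 = 0.59), but not for one rate per class (1 − 0.64 = 0.36). Nor is 1 − 0.99⁴ = 3.9% the relevant family error, because it counts upper-tail rejections that could never support a claim of being below 5%.

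What does not stand is that the point then disappears. With one rate per class, joint power is 0.64, still below 80%. Reporting the classes in separate tables, which is already planned, is not a rule for judging the objective. The mismatch between 6.2 and 10.2.1 makes the missing rule more important.

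**Conclusion.** The concern holds in a limited form. The stated 80% is the power of a single comparison. It is not the power for the objective on any reading that needs both drug classes, and the SAP has no success rule.

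At face value, joint power is 0.64 for one rate per class. For all four rates it is about 0.41 under independence, and 0.36 to 0.64 with independent groups and any dependence within a group. At the alpha, limit and sample size actually stated, it is about 0.14 for two independent comparisons and about 0.02 for four, because per-comparison power is about 0.37. These last figures combine this point with the unreproduced sample size and should not be put down to the missing rule alone. They assume 387 evaluable patients per rate and true rates of 2.5%.

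If any one success may be claimed, the one-directional error is up to about 2%. The documents do not support saying that all four passes are required, that the study will probably fail for this reason alone, or that the 80% was offered as the chance of overall success.

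**What to change.** In sections 6.2 and 10.2.1, state in advance which rates (false negative, false positive, per class) must be shown below 5% for the objective to be met, and what is concluded if only some are. Reconcile this with the true negative rates named as the primary variable in 10.2.1. The choice of rule is the sponsor's. A rule requiring every rate needs no alpha split; a rule allowing any one success needs one (for four tests, for example, 0.01/4 = 0.0025 two-sided each).

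Label the power as per comparison and give the joint power beside it with the dependence assumption. Compute both from the power that the stated alpha, null value and sample size deliver. Relabelling the present figure as 80% per rate would repeat a number that those inputs do not give.

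The cost is SAP wording and a less favourable stated power, with no extra patients. Keeping 80% jointly on four independent rates at the stated alpha and 5% limit would instead need about 1055 evaluable per group (1055/0.88 = 1199 enrolled). That figure is given for scale and is not proposed here.

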6.2 Study Objectives

[figure not shown]
6.2.1 Primary Objective

- Assess the diagnostic performance of the IVD DOAC Dipstick test for oral direct Factor Xa and Thrombin inhibitors from urine samples of patients in comparison to the results of the concentration of the DOACs determined by liquid chromatography mass spectrometry (LC-MS/MS)

Confidentiality Statement

This document is confidential and proprietary to Sponsor and HLZ Medizinische Statistik and for restricted circulation and access only. No part of it may be transmitted, reproduced, published or used by any person/s without prior written authorization.

The flow chart for adjudication of eligible patients to group A (factor Xa inhibitors) and thrombin inhibitors is shown in the following figure:

6.2.2 Secondary Objectives

- Comparison of the investigator-assessed POCT results with the results obtained by reflectance photometric reading (DOASENSE Reader)
- Determination of the inter-centre reliability of DOAC Dipstick test at centres including a minimum of 30 patients.
- Determination of the sensitivity and specificity of the results of the reflectance photometric reading (DOASENSE Reader) by means of concentrations of Rivaroxaban, Apixaban, Edoxaban and Dabigatran determined by LC-MS/MS
- Investigate the handling and usability of the IVD for oral direct Factor Xa and Thrombin inhibitors in clinical setting using a questionnaire for the investigator / sub-investigator.

Confidentiality Statement

This document is confidential and proprietary to Sponsor and HLZ Medizinische Statistik and for restricted circulation and access only. No part of it may be transmitted, reproduced, published or used by any person/s without prior written authorization.

6.2.3 Premature discontinuation of the Post Marketing Study

The sponsor has the right to terminate the entire Post Marketing Study or parts thereof at any time.

The investigator has the right to terminate participation in the Post Marketing Study at any time.

A premature termination must be discussed between the involved parties before becoming effective.

There are no statistical criteria for clinical investigation termination.

6.2.4 Patient identification

The medical records at the investigational site will identify patients. No screening log of patients is included in the study.

With signing of informed consent, the patients will be assigned a specific identification number for the Post Marketing Study (2-digits for the study center followed by a 3-digit code for patients starting by 001 with consecutive number for every new patient having signed the informed consent.

The investigator will maintain a patient identification log, which lists all patients enrolled in the Post Marketing Study, with an identification code linked to their names, alternative identification or contact information. This list will not be provided to the sponsor.

Patients who withdraw consent at any time after signing informed consent are counted as drop out and data will be or not transferred to the data manager or will be eliminated by

6.2.5 Identification, traceability and labelling of the *In vitro* Diagnostic Test

Table: DOAC urine test strip

Name:	DOAC Dipstick
Manufacturer:	DOASENSE GmbH, Heidelberg
Model/Type:	DOASENSE REF Number: 0001

Confidentiality Statement

This document is confidential and proprietary to Sponsor and HLZ Medizinische Statistik and for restricted circulation and access only. No part of it may be transmitted, reproduced, published or used by any person/s without prior written authorization.

Lot number:	DS 18021901
Expiration date:	2019 05 as of December 2018
Intended use:	Analysis of the presence or absence of DOACs in urine and of normal or low concentration of creatinine
Contraindications:	known intolerance to DOACs
CE certification:	CE marked DIMDI registration number: DE/CA 38/00141004
Packaging:	Container (12 test strips) including reference color chart

CE: Certification (Conformité Européene [European Conformity])

DOAC: Direct oral anticoagulant

The packaging and the instructions for use will indicate that the device is only intended for the Post Marketing Study according to this Study Plan.

The sponsor will supply the investigators and clinical investigation sites with the test, including all relevant documentation.

Used test strips will be discarded into the standard containers of the site for collection of tubes containing blood or urine samples. Unused test strips will be returned to the sponsor.

